1 SYNOPSIS

Protocol Title:	CLBP Single-Arm Long-term Follow-up Study
Protocol Number:	CD_3030_ Rev A
Sponsor:	Relevant Medsystems, Inc.
Objectives	The objective of this study is to evaluate the long-term effectiveness of the Intracept® Intraosseous Nerve Ablation System for the treatment of chronic low back pain (CLBP) in typical spine practices.
Regulatory Status	The Intracept® Intraosseous Nerve Ablation System is FDA 510(k) cleared and CE Marked for the ablation of basivertebral nerves of the L3 through S1 vertebrae for the relief of chronic low back pain of at least 6 months' duration that has not responded to at least 6 months of conservative care, and is also accompanied by features consistent with Type 1 or Type 2 Modic changes on an MRI such as inflammation, edema, vertebral endplate changes, disruption and fissuring of the endplate, vascularized fibrous tissues within the adjacent marrow, hypointensive signals (Type 1 Modic change), and changes to the vertebral body marrow including replacement of normal bone marrow by fat, and hyperintensive signals (Type 2 Modic change).
Study Design	This is a prospective, noninterventional, observational post market data collection of long-term effectiveness and satisfaction outcomes for the A Prospective, Open-Label, Single-Arm Study of Intraosseous Basivertebral Nerve Ablation for the Treatment of Chronic Low Back Pain (CLBP Single-Arm Study) population collected at three (3), four (4), and five (5) years post Intracept Procedure. Study sites will ask subjects about their interest in participating in this follow-up study. If a subject agrees to be contacted about participation the site will provide the subject's contact information to an independent clinical research associate (CRA) who will then obtain verbal informed consent. After consent is obtained, the independent CRA will collect the study data at three scheduled telephone study visits. Data will be analyzed by a third-party statistician.
Number of Subjects	47 subjects treated in original CLBP Single-Arm study will be given the option to participate in the study.
Number of Sites	Two (2) sites in the US

Efficacy Assessments	
The following pain, function, and low back pain (LBP) treatment measurements will be collected at each telephone study visit:
 
• Oswestry Disability Index (ODI)• LBP numeric pain score (NPS), Scale 0 to 10• Opioid use for LBP in past 30 days• Injections for LBP in the past 12 months• Lumbar back interventions since last study visit• Return to activity and work status• Satisfaction survey

2 LIST OF ABBREVIATIONS

510(k)	Premarket Notification, per FDA
AE	Adverse events
BVN	Basivertebral nerve
CE mark	Required for a medical device to be sold in the EU
CLBP	Chronic Low Back Pain
CRC	Clinical Research Coordinator
CRA	Clinical Research Associate
CRF	Case report form
eCRF	Electronic case report form
FDA	Food and Drug Administration
GCP	Good Clinical Practice
HIPAA	Health Insurance Portability and Accountability Act
ICH	International Conference on Harmonisation
ID	Identification
IRB	Institutional Review Board
ISO	International Organization for Standardization
ITT	Intent-to-Treat
L3, L4, L5	Lumbar vertebral levels
LBP	Low back pain
LSM	Least squares mean
MCID	Minimal clinically important difference
MRI	Magnetic resonance imaging
NPS	Numeric Pain Score
ODI	Oswestry Disability Index
PP	Per protocol
RF	Radiofrequency
RCT	Randomized Controlled Trial
S1	Sacral vertebral level one
SAE	Serious adverse event
US	United States of America
VAS	Visual Analog Scale pain tool

3 INTRODUCTION – CLINICAL EXPERIENCE TO DATE

Recent studies have demonstrated that vertebrogenic pain from degenerated or damaged vertebral endplates is an important source of chronic low back pain (CLBP).¹⁻⁶ Vertebral endplate damage can lead to cellular communication between the disc nucleus and the bone marrow, triggering inflammation in the intraosseous space.⁴ The basivertebral nerve (BVN) within the vertebral body has nociceptors that receive pain signals from the damaged and inflamed endplate and transmit these pain signals to the central nervous system. Endplate damage and inflammation of the intraosseous space are visible as Modic changes on Magnetic Resonance Imaging (MRI).⁴

The Intracept device is a minimally-invasive intervention using a transpedicular approach to deliver radiofrequency (RF) energy to ablate the BVN. Once ablated, these nerves no longer transmit pain signals. The Intracept® Intraosseous Nerve Ablation System is FDA 510(k) cleared and CE Marked for the ablation of basivertebral nerves of the L3 through S1 vertebrae for the relief of chronic low back pain of at least 6 months duration that has not responded to at least 6 months of conservative care, and is also accompanied by either Type 1 or Type 2 Modic changes on MRI.

Following a successful pilot study⁷, three additional studies were conducted on the Intracept Procedure - two level 1 randomized controlled trials (RCT) and one single arm study:

3.1 SMART Trial:

- The SMART trial was a randomized, double-blinded, sham-controlled, multicenter, international, investigational device exemption (IDE) trial. It was conducted between 2011 to 2014 and enrolled 225 subjects at 15 sites (N=202) in the United States (US) and 3 sites (N=23) in Europe.⁸ The primary requirements for inclusion in the trial were CLBP with a duration greater than 6 months; CLBP non-responsive to at least 6 months of non-surgical management; and Modic Type 1 or 2 changes at the vertebral endplates of the levels targeted for treatment.
- The primary efficacy endpoint for the original study was the 3-month change in Oswestry Disability Index (ODI) compared between the study arms. This comparison, as previously reported,⁸ found that at 3 months the per-protocol (PP) treatment group exhibited a 20.5 Least Squares Mean (LSM) improvement in ODI compared to a 15.2 LSM improvement in the sham group ($p = 0.019$). The PP treatment arm subjects exhibited a durable ODI mean improvement (23.4 points) at 24 months.⁹
- In terms of percent improvement in ODI from baseline, these results translate into mean percentage improvements of 46.2% at 12 months and 53.7% at 24 months. Responder rates for ODI and LBP visual analogue scale (VAS) were also maintained through two years, with patients showing clinically meaningful improvements in both: ODI \geq 10-point improvement in 76.4% of patients and ODI \geq 20-point improvement in 57.5%; VAS \geq 1.5 cm improvement in 70.2% of patients. Patients receiving the Intracept Procedure also decreased utilization of opioids and spinal injections as compared to utilization prior to treatment.
- Clinically significant outcomes of pain reduction and functional improvement were sustained in the treatment arm US subjects through a mean follow-up of 6.4 years. Mean ODI score improved from 42.81 at baseline to 16.86 at 5-year follow-up, a reduction of 25.95 points ($p < 0.001$). Mean reduction in VAS pain score was 4.38 points (baseline of 6.74,

$p < 0.001$). In total, 66% (66/100) of patients reported a $> 50\%$ reduction in pain, 47% reported a $> 75\%$ reduction in pain, and 34% of patients reported complete pain resolution. Composite responder rate using thresholds of ≥ 15 -point ODI and ≥ 2 -point VAS for function and pain at 5 years was 75%.¹⁰

3.2 INTRACEPT Study:

- This prospective, parallel, open-label, randomized controlled study conducted in 20 US sites, compared the effectiveness of intraosseous RF ablation of the BVN (BVN Ablation) to standard care for the treatment of CLBP in patients with primary vertebrogenic-CLBP. A total of 140 patients (66 BVN ablation and 74 standard care) with CLBP of at least 6 months duration, with Modic Type 1 or 2 vertebral endplate changes between L3 to S1, were randomized 1:1 to undergo either RF ablation of the BVN or continue standard care. The primary endpoint was a between-arm comparison of the mean change in ODI from baseline to 3 months post-treatment. Secondary outcome measures included LBP pain scores via VAS, combined ODI and VAS responder rates, SF-36, and EQ-5D-5L at 3, 6, 9, and 12-months post-procedure. An interim analysis to assess for superiority was prespecified and overseen by an independent data management committee (DMC) when a minimum of 60% of patients had completed their 3-month primary endpoint visit.
- The interim analysis showed clear statistical superiority ($p < 0.001$) for all primary and secondary patient-reported outcome measures in the BVN ablation arm compared to the standard care arm. This resulted in a DMC recommendation to halt enrollment in the study and offer early cross-over to the control arm. As a result, the study reported the outcomes of the 104 patients included in the intent-to-treat (ITT) analysis of the 3-month primary endpoint, which included 51 patients in the BVN ablation arm and 53 patients in the standard care arm. At baseline, the mean age was 50 years, mean ODI was 46.1 (severe pain disability) and mean VAS was 6.67 cm (on a 0 to 10 cm scale). More than 67% of patients reported experiencing LBP for greater than 5 years and more than 70% had received prior injections at baseline.
- Comparing the BVN ablation arm to the standard care arm, the mean changes in ODI at three months were -25.3 points versus -4.4 points, respectively, resulting in an adjusted difference of 20.9 points ($p < 0.001$); mean changes in VAS were -3.46 versus -1.02, respectively, an adjusted difference of 2.44 cm ($p < 0.001$).
- In the BVN ablation arm, 74.5% of patients achieved the minimal clinically important difference (MCID) of ≥ 10 -point improvement in ODI, compared with 32.7% in the standard care arm ($p < 0.001$). With a MCID of 2.0 cm improvement in VAS, 72.5% of patients in the BVN ablation arm reached clinical success compared to 34.0% of patients in the standard care arm ($p < 0.001$). No BVN ablation patients received a spinal injection prior to the 3-month endpoint, while in the standard care arm, 6 standard care patients (11%) received injections across 5 study sites.
- The study concluded that minimally invasive RF ablation of the BVN leads to significant improvement of pain and function at 3-months in patients with chronic vertebrogenic-related LBP.¹¹
- The study also concluded that clinically significant outcomes of reduced pain and improved function are sustained through 12 and 24 months post BVN ablation. The 61 BVN ablation arm subjects with a 12 month visit demonstrated a 25.7 ± 18.5 point reduction in mean ODI

($p<0.001$), and a 3.8 ± 2.7 cm VAS reduction ($p<0.001$) from baseline at 12 months, with 64% demonstrating $\geq 50\%$ reduction in pain and 29% pain free. Similarly, the former SC patients who elected BVN ablation 61 (92%) demonstrated a 25.9 ± 15.5 point mean ODI reduction ($p<0.001$) from baseline at 6 month post-BVN ablation.¹² In the 58 BVNA patients completing a 24-month visit, ODI and VAS improved 28.5 ± 16.2 points (from baseline 44.5; $p<0.001$) and 4.1 ± 2.7 cm (from baseline 6.6; $p<0.001$), respectively. A combined responder rate of ODI ≥ 15 and VAS ≥ 2 was 73.7%. A $\geq 50\%$ reduction in pain was reported in 72.4% of patients and 31.0% were pain-free at 2 years.¹³

3.3 A Prospective, Open-Label, Single-Arm Study of Intraosseous Basivertebral Nerve Ablation for the Treatment of Chronic Low Back Pain (CLBP Single-Arm Study):

- A prospective, single-arm, open label study was completed to evaluate the effectiveness of intraosseous RF ablation of the BVN for the treatment of vertebrogenic related CLBP in typical spine practice settings using permissive criteria for study inclusion. Forty-seven (N=47) consecutive patients with CLBP of at least 6 months duration and with Modic Type 1 or 2 vertebral endplate changes between L3 to S1, were treated with RF ablation of the BVN in up to 4 vertebral bodies. The primary endpoint was patient-reported change in ODI from baseline to 3 months post-procedure. Secondary outcome measures included change in VAS, SF-36, EQ-5D-5L, and responder rates.
- An analysis was conducted when 28 treated patients had completed their 3-month primary endpoint visit. Results of this interim analysis of N=28 patients showed mean change in ODI at three months post treatment was -30.07 ± 14.52 points ($p<0.0001$); mean change in VAS was -3.50 ± 2.33 ($p<0.0001$). Ninety-three percent (93%) of patients achieved a ≥ 10 -point improvement in ODI and 75% reported ≥ 20 -point improvement. Because the results were significant for all primary and secondary endpoints, and the co-occurring INTRACEPT RCT had recently been halted for superiority, new enrollments in the CLBP Single Arm Study were stopped.¹⁴
- The full cohort (N=47) was followed for 12 months post BVN ablation and improvements in pain and function remained significant.¹⁵ Forty-five (N=45) (95.7%) subjects completed a 12-month follow-up visit. Mean reduction in ODI at 12 months was 32.31 ± 14.07 ($p<0.001$) with 88.89% (40/45) patients reporting a ≥ 15 point ODI decrease at 12 months. Mean VAS pain score decrease was 4.31 ± 2.51 at 12 months ($p<0.001$) and more than 68% reported a 50% reduction in VAS pain scale. Minimally invasive RF ablation of the BVN demonstrated a significant improvement in pain and function in this population of real-world patients with chronic vertebrogenic-related LBP out to 12 months.¹⁵

The purpose of this study is to measure the long-term effectiveness outcomes at 3+, 4 and 5 years post treatment in subjects treated with the Intratect Procedure in the original A Prospective, Open-Label, Single-Arm Study of Intraosseous Basivertebral Nerve Ablation for the Treatment of Chronic Low Back Pain Single-Arm described above in section 3.3.

4 STUDY DESIGN

4.1 Overview

The CLBP Single-Arm Long-Term Follow-up study is a prospective, noninterventional, observational post market data collection of the effectiveness, ongoing safety, and satisfaction

outcomes for patients previously treated with the Intracept Procedure. This trial will be conducted according to Good Clinical Practice (GCP) guidelines, including participant verbal informed consent and Independent Review Board (IRB) approval and oversight.

4.2 Objective

To evaluate the long-term effectiveness outcomes of the Intracept Procedure for the relief of chronic low back pain in the original CLBP Single-Arm Study patients.

4.3 Scope and Study Population

The 47 subjects who received the Intracept procedure in the original CLBP Single-Arm Study will be contacted and given the option to participate in this study.

4.4 [REDACTED]

[REDACTED]

5 PROTOCOL

This study involves contacting original CLBP Single-Arm Study subjects to seek participation in a data collection of current low back pain, functional status, recent treatments and patient satisfaction. The study will be overseen at each participating study site by a primary investigator and clinical research coordinator (CRC). Telephone visits and data collection will be conducted by an independent study-wide CRA.

5.1 Study Visits

Participants in the study will have three (3) study visits over a period of up to 3+ years based on the timing of their Intracept procedure. Study visits will be conducted via telephone by an independent CRA. Participants will provide verbal informed consent and then answer study questions via telephone study visits at 3+ years, 4 years, and 5 years post Intracept Procedure.

Study subjects who received treatment in the original CLBP Single-Arm Study are eligible to participate in this long-term follow-up data collection. Each study site will make initial contact with the prior study subject and discuss the follow-up study to discern if the subject is interested in participating. The same unique subject ID number used in the CLBP Single-Arm Study will be assigned to the subject. Study participant logs will include subject ID, date(s) of contact and date of agreement/declination to participate and will be maintained by the study site and independent CRA.

Upon subject agreement to participate in the study, the site CRC will forward subject contact information to the independent CRA who will contact the subjects, obtain verbal informed consent, and schedule the telephone study visit. The independent CRA will conduct the telephone study visit, be responsible for the collection of all data elements, and enter data into the designated clinical database.

Study Exit

Subjects will be considered to have completed the study after the 5-year follow-up visit is complete.

5.2 Study Withdrawal/Termination

A subject may withdraw from the study at any time if he/she no longer wishes to participate. If subjects elect to withdraw or is terminated from the study, the independent CRA should inquire about the reason and document details accordingly on the study completion CRF.

If a subject does not respond to at least three documented contact attempts such that the follow-up visit does not occur, the visit will be documented as a "missed visit". Subjects who miss a follow-up visit should still be contacted again for their next scheduled study visit. It is important that continued attempts be made to re-establish contact at subsequent study visits. A subject should not be deemed lost to follow-up and withdrawn from the study until the independent CRA has documented sufficient efforts at achieving subject contact or until the 5-year follow-up study visit window closes for the last subject who received the Intracept procedure.

6 ENDPOINTS

6.1 Primary Effectiveness Endpoint

The primary effectiveness endpoint for this study is the mean improvement in ODI from baseline to 5 years post Intracept treatment.

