6.2 Secondary Effectiveness Endpoints

Secondary effectiveness endpoints are:

- a) The mean improvement in ODI from baseline to 3 years post treatment
- b) The mean improvement in ODI from baseline to 4 years post treatment
- c) The mean reduction from baseline VAS in patient reported pain score (10-point VAS-based numeric pain score) to each timepoint

- d) The number and proportion of subjects in each quartile ($\leq 24\%$ or less, 25-49%, 50-74%, and 75-100%) for percent pain score reduction in low back pain from baseline at each timepoint
- e) Responder rates for ODI: proportion of subjects who achieve ≥ 10 -Point, ≥ 15 -point and ≥ 20 -point reduction in ODI from baseline for each timepoint
- f) Responder rates for pain rating: proportion of subjects who achieve a ≥ 2.0 -point reduction in pain score from baseline for each timepoint
- g) Composite responder rate at each timepoint defined as:
 - 1) ODI decrease of ≥ 15
 - 2) NPS decrease of ≥ 2
- h) Composite responder rate at each timepoint defined as:
 - 1) ODI decrease of ≥ 15
 - 2) NPS decrease of greater than 50%
- i) Composite endpoint of long-term treatment success at each timepoint defined as:
 - 1) ODI decrease of ≥ 15
 - 2) NPS decrease of ≥ 2
 - 3) No injections for the same low back pain etiology and location as treatment location
 - 4) No pain intervention or surgery for the same low back pain etiology and location as treatment location
- j) The number and proportion of subjects with surgical interventions for low back pain of the same treatment region post the Intratect procedure at each timepoint
- k) The number and proportion of subjects actively utilizing (defined as $>25\%$ of total dosage in 30 days prior to study visit) opioids for low back pain of the same treatment region at each timepoint
- l) The number and proportion of subjects utilizing injections since the last study visit for low back pain of the same treatment region at each timepoint
- m) Work impact: number of missed workdays in past 30 days at each timepoint and number of days in bed in past 30 days
- n) Patient satisfaction with the Intratect Procedure at each timepoint

Ongoing safety will be evaluated at each time. SAEs potentially related to the procedure, device, or the spine will be reported and evaluated for relatedness.

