7 STATISTICAL ANALYSIS

7.1 Statistical Methods

The mean change in ODI from baseline to five years is the primary endpoint for this study. Baseline is defined as the last non-missing assessment at or before the baseline visit and prior to the Intratect treatment from the original CLBP Single-Arm Study.

Statistical tests will be two-sided and will be performed at the 0.05 level of significance. Statistical differences will be tested using Student's t-tests. An analysis of covariance (ANCOVA) will also be performed using baseline ODI measurements for the primary endpoint. Baseline NPS will be used as a covariate for the secondary pain reduction endpoint. No other planned analyses will include covariates.

Descriptive statistics will be used for secondary endpoints and will include the number and percentage of subjects in each category. For continuous parameters, descriptive statistics will include n (number of subjects), mean, SD, median, minimum, maximum, and confidence intervals.

Results will be for observed values only. No imputations will be made for missing data.

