8.5 Injections & Interventions

Patient-reported injections and interventions (i.e. RF ablations) for low back pain since the Intratect procedure or last study visit will be collected. Date, type, and location on back of each injection or intervention will be recorded.

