8.7 Injections, Interventions, and Surgeries Adjudication

An independent physician will review all available medical records and radiologic images obtained by the study site to determine diagnosis (pain location, etiology, and nature) resulting in an intervention (procedure and/or injections) or surgery. All interventions and surgeries will be adjudicated as either a treatment failure (ongoing or exacerbated CLBP of similar location, anatomy, etiology /pain source, and nature/severity to the pre-Intracept treatment pain) or not related (different location, anatomy, etiology/pain source, or nature/severity). The independent physician will also review all medical records and radiologic images obtained by the study site to determine or evaluate reported adverse events.

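### Later re-treatment is collected over conflicting look-back periods, and the treatment-failure adjudication is not carried into responder rates (e) to (h)

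*Combined protocol and SAP*

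**What the plan says.** **Main analysis.** Section 6.1 defines the primary endpoint as "the mean improvement in ODI from baseline to 5 years post Intracept treatment". Section 7.1 adds "Results will be for observed values only" and rules out imputation. Neither section excludes, censors or re-scores a subject who is treated again.

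**Collection of re-treatment.** The efficacy assessments in the synopsis ask about injections over the preceding 12 months, and about lumbar interventions since the last visit. Section 8.5 collects "Patient-reported injections and interventions (i.e. RF ablations) for low back pain" from the Intracept procedure or the last visit onward. Endpoint (l) in section 6.2 reports "The number and proportion of subjects utilizing injections since the last study visit".

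**Adjudication.** Section 8.7 states: "All interventions and surgeries will be adjudicated as either a treatment failure", defined as "ongoing or exacerbated CLBP of similar location, anatomy, etiology /pain source, and nature/severity to the pre-Intracept treatment pain", or as not related if any of those features differs.

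**Use in endpoints.** Only composite (i) in section 6.2 combines scores with absence of re-treatment. Its third component covers injections, and its fourth reads "No pain intervention or surgery for the same low back pain etiology and location as treatment location". Endpoint (j) reports "The number and proportion of subjects with surgical interventions for low back pain of the same treatment region". The ODI, pain and composite responder rates in (e) to (h) are defined by scores alone.

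**The concern.** The study has no comparator, so what a reader learns about durability depends on seeing how much later treatment the cohort received. Two features of the plan obscure this.

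First, the injection item has two incompatible recall periods. If the telephone worksheet follows the synopsis, injections between the end of the earlier follow-up and the last 12 months before the first call are never asked about. Missed injections can only lower (l). They can only raise (i) or leave it unchanged, because each one is a failure that is not recorded.

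Second, an independent physician decides whether each later intervention marks failure of the treatment, but the visible plan gives that decision no stated role. A subject adjudicated as a failure at year 4 can be a responder at year 5 in (e) to (h). Composite (i) resembles the adjudication but does not cite it and uses different criteria. Procedures that are neither surgery nor injection enter (i), but no endpoint counts them separately, so the extent of re-treatment cannot be read from the planned results.

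**Working it through.** The plan gives no figure to reproduce on this point. The check sets the texts side by side, then illustrates the possible size.

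**1. Look-back at the first call.** Inputs: the earlier study is described to 12 months (section 3.3), and the first call is at 3+ years (section 5.1), so T is at least 36 months. Let S be the month from which the history should start. A 12-month question covers months T − 12 to T, so the unasked period is T − 12 − S.
- If the last visit is the 12-month visit, S = 12. At T = 36 the gap is 36 − 12 − 12 = 12 months, half of the 24-month interval.
- If the history runs from the procedure, S = 0. The gap is 36 − 12 − 0 = 24 months, though part of it may already have been recorded in the earlier study.
- A later first call widens the gap month for month.

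If injections were spread evenly over months 12 to 36 (an assumption), half of the injections would be missed, and at most half of the injected subjects, since some have repeats. The gap can recur. Section 5.2 keeps subjects in the study after a missed visit, so someone seen at years 3 and 5 only has 24 months since the last visit, of which a 12-month question covers 12.

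**2. Composite (i) against section 8.7.**

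| | Criteria for a related event |
|---|---|
| (i), components 3 and 4 | same etiology and location |
| 8.7, treatment failure | similar location, anatomy, etiology or pain source, and nature or severity |

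An event of the same etiology and location but different severity fails (i) as worded, yet is not related under 8.7. Conversely, similar is looser than same. The two rules can therefore disagree in either direction.

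**3. What (i) covers.** Its score components match those of (g), so it is a re-treatment-adjusted counterpart to (g). It is not a counterpart to (e) or (f), which use single-measure thresholds, or to (h), which needs more than 50% pain reduction.

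**4. Possible effect on a responder rate (illustration).** The documents give no re-treatment rate and no 5-year number analysed. As a stand-in, take the 12-month result in section 3.3: 40 of 45 with an ODI decrease of at least 15 points (40/45 = 88.9%), hence 5 non-responders. Suppose k of the 45 are adjudicated failures and are counted as non-responders, with the denominator kept at 45. The number of responders re-coded lies between max(0, k − 5) and k.

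| k (assumed) | Responders left | Rate |
|---|---|---|
| 2 (4%) | 38 to 40 | 84.4% to 88.9% |
| 5 (11%) | 35 to 40 | 77.8% to 88.9% |
| 9 (20%) | 31 to 36 | 68.9% to 80.0% |

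**5. Significance.** The 12-month mean change was 32.31 (SD 14.07, n = 45), so t = 32.31/(14.07/√45) = 15.4. Even if 9 of the 45 had zero change and the other 36 kept that mean and SD, the mean would be 36 × 32.31/45 = 25.85 with SD 18.12, and t = 25.85/(18.12/√45) = 9.57. The test against zero is not at risk in this range.

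**The case against.** The strongest reply is that the plan already tells an analyst what to compute. Sections 6.1 and 7.1 contain no exclusion, so observed scores are used throughout. The synopsis sets the objective in typical spine practices, and outcome regardless of later care fits that. This stands. A reader might infer that the primary estimate is undefined or invalid because post-treatment care is mixed in; the documents do not support that.

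A reader might also infer that the plan needs a primary mean with failures set to zero change. That overcorrects. With 9 of 45 re-treated and re-treatment adding 10 points (the MCID in section 8.1), the observed mean moves by 9/45 × 10 = 2.0 points, whereas setting those subjects to zero removes 32.31 − 25.85 = 6.46 points. The two agree only if re-treatment supplied the whole improvement. Such a mean is a worst-case score and should not be required.

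It can further be said that 8.5 already asks for the full history, that medical records may recover missed injections (sections 8.7 and 10.4), and that (i) handles re-treatment. Each is partly right. Section 8.5 does not cancel the contrary instruction in the synopsis. Records depend on a release from the subject (section 10.3) and may not be sought for an event that was never reported. Composite (i) covers one responder definition, states no look-back, and departs from the adjudication criteria.

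**Conclusion.** The point holds as a matter of consistency in capture and use of re-treatment; the main analysis is sound as planned. The look-back conflict is a plain contradiction. If the synopsis governs, at least 12 months of injections go unasked at the first call, with a known direction: (l) too low, (i) too high or unchanged. The missing link between 8.7 and (e) to (h) leaves responder rates that can include adjudicated failures, with no count showing how many.

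The size is unknown. The responder ranges rest on assumed failure shares of 4% to 20% and on 12-month results standing in for 5 years. The direction of any effect on mean ODI is also open, since re-treated subjects may have improved because of it or may have done worse than the rest. No change in significance against zero is expected, and none should be inferred. Section 4.4 is redacted, so statements of absence apply to the visible text only.

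**What to change.** 1. Reconcile the injection look-back in the synopsis with section 8.5 and endpoint (l). The first call should cover the whole period since the last visit of the earlier study, and (i) should be able to use the history since the procedure.
2. State that components 3 and 4 of (i) are decided by the section 8.7 adjudication, and align the wording of the two.
3. At each timepoint, report the number of subjects with any adjudicated treatment failure, including non-surgical interventions such as RF ablation, and the number whose intervention could not be adjudicated.
4. Keep the observed-value main analysis in section 7.1, and say that it uses scores regardless of later treatment. Add one supplementary analysis that counts subjects with an adjudicated failure since the procedure as non-responders in (e), (f) and (h), using the same denominator as the observed-value rates. Show (i) beside (g). Give mean ODI change separately for subjects with and without an adjudicated failure, as description only, because the groups are formed by events after treatment.

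The cost is a few sentences and one extra table, from data and adjudication already planned. The supplementary rates may be less favourable, and they are conservative for a re-treated subject who kept some benefit from Intracept.
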